2.1. Summary Data Collection and Schedule of Events

Data will be collected on electronic case report forms at the pre-procedure, index procedure and post-procedure visits. A schedule of the study activities by visit is provided below.

 Table 1 Schedule of Study Activities by Visit:

Visit	Selection/	Proce-	arb	Dis-	3 months	Unsched-
	Inclusion	dure	24h	charge	FU	uled visit ²
Patient Demographic	Х					
Patient informed consent	Х					

Incl/excl criteria	х					
Clinical status	Х		Х	Х	Х	Х
(mRS ³ , NIHSS ⁴)						
Quality of Life					Х	Х
Medical history	Х					
Relevant concomitant	Х					Х
medication						
Procedure		х				
Antiplatelet and antico-		х				
agulant therapy ¹						
Procedure complications		х				
Procedure results		х				
AE(s)		Х	х	Х	х	Х
CT/MRI	X		х			Х

NOTES:

1 To be administered just before procedure

2 Any data collected based on the reason for unscheduled visit

3 Performed by an independent neurologist

4 Selection, 24h, Discharge

3 Introduction

Acute ischemic stroke (AIS) remains the leading cause of long-term disability in the United States with approximately 795,000 individuals afflicted in the United States every year.[1] Direct medical costs of stroke are upwards of \$17 billion, and the cost in terms of human suffering remains high, with more than 50% of stroke patients requiring discharge to a rehabilitation or skilled nursing facility. Up to one half of AIS is related to emergent large vessel occlusion, most commonly of the internal carotid artery (ICA) or middle cerebral artery (MCA). Until recently, intravenous tissue plasminogen activator given within 4.5 hours of symptom onset was the only treatment approved by the US Food and Drug Administration, and early randomized trials of endovascular stroke therapy failed to demonstrate benefit. More recently, however, multiple trials have now unequivocally established the clinical benefit associated with mechanical thrombectomy for certain well-

selected patients. The improved results observed in these trials were due to both increased understanding of patient selection as well as the use of newer, more effective treatment devices.[1-8]

Early recanalization of the occluded artery leads to improved clinical outcomes in patients with AIS, most likely through protection of the penumbra. If timely recanalization can be achieved and reperfusion established, damage to the penumbra region may be prevented, thus resulting in improved neurological outcome with less deficits and a reduction in stroke-related mortality and morbidity. [4, 9-15]

Recently, first-line, direct-aspiration first-pass technique performed with new thrombectomy devices generated promising results in several retrospective studies. This distal suction system, with a high level of endovascular navigability, provided high recanalization rates (up to 97%) with low morbidity and good functional outcomes.[12, 16-20] Patients treated with first-line, direct-aspiration first-pass technique versus mechanical thrombectomy using a stent retriever achieved higher final recanalization rates but adjunctive devices or rescue procedures had to be used more frequently [20].

Our research aims to show that a first line strategy of recanalization by thrombectomy using a distal suction system provides fast recanalization by sole aspiration with good safety and Effectiveness. Thus, the primary aim of this study is to assess the safety and effectiveness of the SO-FIA[™]/SOFIA[™] PLUS catheter for direct aspiration as a first line treatment technique (SESAME) in patients with acute ischemic stroke from large vessel occlusion.

4 Study Overview

4.1. Study Design

This is a multi-center, single arm, prospective, observational registry of the SOFIATM/ SOFIATM PLUS Catheter in Europe. Consecutive patients presenting within 6 hours of symptom onset with an anterior circulation large vessel occlusion (LVO) acute ischemic stroke (within the internal carotid artery and internal carotid terminus, middle cerebral $-M_1/M_2$ segments) will be treated using aspiration thrombectomy as first intention and site routine practice. Devices received CE-mark and will be used according to the 'Instructions For Use'.

The follow-up visits will occur at 24 + - 12 hours, at patient discharge, and 90 + - 14 days post-procedure.

Furthermore the study design is adaptive, prospectively stating interim analyses with specified stopping rules, which allow for the possibility of the study to terminate early based on either a determination of study success or of the futility to continue further enrollment.

4.2. Endpoints

The primary objective of this study is to observe the percentage of good clinical outcomes defined as ≤ 2 at 90 days.

4.2.1. The primary endpoint

Primary endpoint of the study will be mRS \leq 2 at 90 days as assessed by an independent neurologist)

4.2.2. The secondary endpoints

Safety endpoints:

- The occurrence of major neurological events (stroke, intracranial hemorrhage, intracerebral hemorrhage, etc.) prior to discharge
- Devices and procedure related adverse events within 90 days of follow up
- Occurrence of embolization in previously uninvolved (or new) territories (ENT) as seen on the final control angiogram at the end of the procedure
- Occurrence of symptomatic intracranial hemorrhages (sICH) within 24 hours
- Occurrence of intracranial vessel damages at the end of the procedure.

Recanalization:

- Proportion of patients having complete recanalization (TICI ≥ 2b) just after first line aspiration treatment compared to historic controls based on published RCTs*
- Proportion of patients having complete recanalization (TICI ≥ 2b) after thrombectomy using an additional device
- Time from groin puncture to complete recanalization (TICI ≥ 2b) in patients after first line aspiration treatment (SESAME).
- Time from groin puncture to recanalization (TICI ≥ 2b) after thrombectomy using an additional device
- Time from CT-scan/MRI at the institution to groin access
- Time from symptom onset to CT-scan/MRI

* assessed by an imaging core lab.

Clinical endpoints / quality of life:

- NIHSS score at 24 hours
- NIHSS score at discharge
- Quality of Life questionnaire at 90 days

4.2.3. Supplemental Endpoints

Imaging endpoints:

• Difference of ASPECT scores in CT/MRI pretreatment vs. 24h

In the subgroup of patients with additional perfusion CT (as per local standard of care):

• Volume of saved brain tissue determined by predictive modeling

Health Economics:

- Device costs (standardized cost of all devices as well as human resources and medication used during index procedure)
- Hospital length of stay

4.3. Study Population

Up to 250 consecutive patients at up to 15 centers in Europe with symptoms of acute ischemic stroke who are eligible for inclusion into this study. The patients must meet the following inclusion criteria and none of the exclusion criteria:

Inclusion Criteria:

- Participant is \geq 18
- Demonstrated occlusion of the distal intracranial carotid artery, middle cerebral artery (M1 or M2) or anterior cerebral artery (A1 or A2) in the anterior circulation proven by CT and/or MRI
- NIHSS ≥ 2 and < 30 at screening
- Start of the thrombectomy procedure within 6 hours of the onset of stroke symptoms
- Pre event mRS ≤ 1
- Patient or patient's legally authorized representative or impartial witness/independent physician has received information about data collection and has signed and dated an Informed Consent Form

Exclusion Criteria:

- Patient is more than 6 hours from symptom onset
- Evidence of cerebral ischemia in the posterior circulation
- Rapidly improving neurologic examination
- Severe unilateral or bilateral carotid artery stenosis requiring stent treatment
- Absent femoral pulses
- Presence of an existing or preexisting large territory infarction
- Excessive vascular tortuosity that will likely result in unstable access

- Pregnancy; if a woman is of child-bearing potential and urine or serum beta HCG test is positive
- Known contrast product allergy
- Patient has a severe or fatal comorbidity that will likely prevent improvement or follow-up or that will render the procedure unlikely to benefit the patient
- Evidence of intracranial hemorrhage (SAH, ICH, etc.)

Imaging exclusion criteria:

- Significant mass effect with midline shift or intracranial tumor
- Baseline non-contrast CT or DWI MRI evidence of a moderate/large core defined as extensive early ischemic changes of Alberta Stroke Program Early CT score (ASPECTS) 0-5

4.4. Rationale

Several publications describing the use of aspiration as a first line treatment technique in AIS patients have shown superior technical results with similar clinical outcomes to those seen when using a traditional stent retriever. They have also shown decreased procedure time and cost. The aim of this study is to show similar results in terms of speed, Effectiveness and safety when SOFIATM/ SOFIATM PLUS is the catheter used for first line aspiration thrombectomy.

4.5. Device Description / Principles of Operation

A detailed description of the SOFIA[™]/ SOFIA[™] PLUS catheter is contained in the 'Instructions For Use' for these devices, which have obtained commercial authorization in Europe (CE Mark). Described herein are brief descriptions of the System and the principles of operation.

The SOFIA[™]/SOFIA[™] Plus Catheter is intended for use in removal/aspiration of emboli and thrombi from selected blood vessels in the arterial system in patients with AIS, including the peripheral and neurovasculatures.

4.5.1. Device Description

The SOFIA[™] (Soft Torqueable Catheter Optimized For Intracranial Access) and SOFIA[™] PLUS Catheter are single lumen, flexible catheters, designed with coil and braid reinforcement. The SOFIA[™] / SOFIA[™] PLUS catheters have a soft distal tip for easy navigation in tortuous vessels. The tip is steam shapable and the proximal shaft torquable to help steer around challenging bifurcations. The coil and braid construction provides enhanced kink resistance and 1:1 push / pull control. Once navigated to the site of the occlusion, the SOFIA[™] / SOFIA[™] PLUS catheters can be used in conjunction with an aspiration source, such as a pump or syringe, to facilitate aspiration thrombectomy of the occluded vessel. The SOFIA[™] / SOFIA[™] PLUS catheters have large lumens, developed to maximize aspiration power and capture of thrombus.

Dimension	SOFIA™	SOFIA™ PLUS
French size	5F	6F
Outer diameter	.068"	.0835"
Inner diameter	.055"	.070"
Working lengths	115CM	115CM
	125cm	125CM
		131CM
Compatibility	6F sheaths	6F sheaths
	Guide catheters ≥.070"	BGC ID ≥.085"

SOFIA[™] & SOFIA[™] PLUS key dimensions:

Table 2: Features of the SOFIA™ /SOFIA™ PLUS Catheters

Features	Benefits
Up to 0.070 Inch Lumen	Large lumen for strong aspiration & capture of
	large thrombus
Exceptionally Soft Distal Tip	Allows smooth distal navigation and easy passage
	of bifurcations
Steam Shapeable Tip and Torqueable Shaft	Highly navigable for patients with challenging
	anatomy
Enhanced Kink Resistance	Maintains lumen integrity during navigation and
	aspiration in tortuous anatomy

5 Study Procedures

5.1. Screening

Patients presenting with AIS will be evaluated by the physician to establish an appropriate treatment plan based on the patient's medical condition and available diagnostic screening procedures prior to recruitment in the study. If treatment of the ischemic stroke with a mechanical thrombectomy device is deemed appropriate, the following evaluations will be performed to determine if they meet the inclusion and exclusion criteria. All assessments in the study are made on the basis of good standard of care and not specifically for the study. This applies both to clinical assessments and imaging studies. There are no follow-up requirements for participants who are general eligibility screen failures.

5.2. Informed Consent

Image data acquisition, treatment via interventional procedure with a CE-marked device and clinical evaluation are all considered standard of care and thus there is no need for additional consent. Informed consent for data collection must be obtained prior to enrollment of patients in this study and data transmission.

However, most patients will be unable to give their consent prior to treatment. We expect that approximately 60% of patients will be unable to give informed consent prior to therapy with the SOFIA[™]/ SOFIA[™] PLUS catheter. Excluding this group of patients from the study would entail severe scientific and clinical drawbacks. Results would be biased by systematically excluding more severe strokes and patients with aphasia, i.e. mostly left hemispheric strokes. As a consequence, the generalizability of the study results would be limited.

Once the patient's potential eligibility has been determined, the Investigator will discuss the study and ask the patient, or the patient's legally authorized representative, based on the site routine practice and regulatory requirements, if they are interested in participating in the data collection. The study will be explained to the consenting person in lay terms. Study personnel should document the consent process in the participant's medical record per Good Clinical Practice (GCP). The participant or legally authorized representative is to be provided a copy of the signed ICF. In case the patient was not able to provide his consent before the procedure, all attempts will be made to obtain his consent before discharge. Additionally, patients who signed an Informed Consent Form but did not meet general inclusion/exclusion criteria should also be recorded in the screen failure log.

5.3. Pre-treatment Assessment

Patient history will include but not be limited to the following risk factors and comorbidities: age, height, weight, gender, hypertension, hyperlipidemia, diabetes mellitus, ischemic heart disease (history of myocardial infarction, angina pectoris, previous stroke, or any cerebrovascular disease), atrial fibrillation, congestive heart failure, peripheral artery disease, current smokers.

- Obtain the time of symptom onset and record it with the time of hospital admission.
- Obtain appropriate non-contrast CT (NCCT and CTA) scans or MRI (and MRA) performed first and record this as well as the time of NCCT/MRI. The ASPECT (or MR DWI-ASPECT) score will be then calculated.
- Neurological examination will include an assessment of the NIH Stroke Scale (NIHSS) within the 2 hours before treatment. NIHSS certified study personnel must determine NIHSS.
- Obtain patient's functional status by assessing his/her modified Rankin Score (mRS prior to stroke onset).

- Physical examination will include recording of supine blood pressure and heart rate.
- Obtain, as routine practice, platelets, glucose and international normalized ratio (INR), partial thromboplastin time (PTT).
- Females who are pregnant or lactating are excluded from the study. A pregnancy test should be ideally administered to all female patients of childbearing potential.
- All potentially stroke impacting concomitant medication will be captured (ASA, anticoagulants, antiplatelet, and hypertensive medications).

5.4. Enrollment

Once all inclusion/exclusion criteria are met, the patient is enrolled when a SOFIA[™]/ SOFIA[™] PLUS Catheter is inserted in the patient and will be assigned a five digit identification number (participant study number). The first two digits assigned represent the site identification, followed by a hyphen and three subsequent digits which represent the sequential enrollment number. For example, ID: 04-002 would represent the second participant enrolled at site 04.

5.5. Procedure

The SOFIA[™]/ SOFIA[™] PLUS Catheter will be used in removal/aspiration of emboli and thrombi following the CE marked Instructions For Use. Enrollment into the study does not change the routine care at the site provided to the patient requiring mechanical thrombectomy treatment. The time of the following events will be recorded for each patient:

- Index stroke symptom onset
- Hospital admission
- Arterial puncture for endovascular intervention
- Pre-procedure TICI score
- Start of aspiration by the SOFIA[™]/ SOFIA[™] PLUS
- End of aspiration by the SOFIA[™]/ SOFIA[™] PLUS
- Time of first TICI 2b or 3
- If an adjunctive treatment is used, time and TICI score after SOFIA[™]/ SOFIA[™] PLUS Reperfusion Catheter has been used
- Last angiogram taken after all treatments at the end of the procedure.

Additionally, the following information will be recorded:

- Location and length of occlusion
- The final TICI after all adjunctive treatments
- Ancillary device and/or adjunctive treatment trade mark and model
- Intraprocedural complications
- Presence of vasospasm (time of onset, vessels involved, time resolved)
- Evidence of clot migration or embolization

- Dissections/ perforations
- Devices deficiencies, malfunction, complaints (including 2nd line devices in case of aspiration failure)
- Antiplatelet therapy regimen
- Sedation

Those patients with improving neurological status prior to endovascular intervention may or may not undergo mechanical thrombectomy at the discretion of the treating physician.

The definition of rapid improvement that leads to foregoing endovascular intervention is at the discretion of the Investigator based on clinical judgment regarding risks versus benefits.

Those patients excluded according to the selection criteria but treated with a SOFIATM / SOFIATM PLUS Catheter will be considered as intent to treat patients.

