9.2.1. Definition of Analysis Samples

All primary and secondary Effectiveness and safety outcome measures will be analyzed under both the intent-to-treat (ITT) and per-protocol (PP) principles.

a) Intent to Treat Sample

The ITT sample includes all participants who are enrolled.

b) Per Protocol Sample

The per-protocol sample will include all participants that do not have the following protocol violations or deviations:

1) Eligibility violation

2) No Sofia/Sofia Plus treatment performed

3) mRS primary effectiveness only: missing 90-day outcome (not including missing due to death prior to the 90 days)

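### Protocol 5.4 with 9.2.1(a) contradicts 5.5 on whether a patient who fails a selection criterion but is treated with SOFIA is enrolled and belongs to ITT

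*Protocol*

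**What the plan says.** Four parts of the protocol bear on a patient who fails a criterion but receives the device.

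- **Enrolment (5.4).** "Once all inclusion/exclusion criteria are met, the patient is enrolled when a" SOFIA or SOFIA PLUS catheter is inserted. The study number is assigned at that moment.
- **Excluded but treated (5.5).** Patients "excluded according to the selection criteria but treated with a SOFIATM / SOFIATM PLUS Catheter will be considered as intent to treat patients".
- **Analysis samples (9.2.1).** For ITT: "The ITT sample includes all participants who are enrolled". For PP: "The per-protocol sample will include all participants that do not have the following protocol violations or deviations", of which the first listed is "Eligibility violation". Both samples carry the whole analysis: "All primary and secondary Effectiveness and safety outcome measures will be analyzed under both the intent-to-treat (ITT) and per-protocol (PP) principles".
- **Screen failures (5.1, 5.2).** Under 5.2, "patients who signed an Informed Consent Form but did not meet general inclusion/exclusion criteria should also be recorded in the screen failure log". Under 5.1, "There are no follow-up requirements for participants who are general eligibility screen failures".

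The synopsis names per protocol alone as the analysis population for the primary and secondary endpoints, which does not match 9.2.1.

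**The concern.** Section 5.4 makes eligibility a condition of enrolment, and 9.2.1(a) makes enrolment the condition for ITT. Section 5.5 assigns to ITT exactly the patients whom that chain leaves out.

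Such patients are foreseeable. Treatment is routine care with a CE-marked device, so eligibility for the registry does not decide who is treated. Section 5.5 itself leaves thrombectomy in patients with improving neurological status to the physician's discretion, while 4.3 lists rapid improvement as an exclusion.

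What is at stake is the denominator. PP omits eligibility violations by design, so ITT is the only one of the two samples that can show outcomes and device-related events in these exposed patients. Timing adds to the problem. Section 5.2 expects about 60% of patients to be unable to consent before therapy, and the informed-consent text in 10.3.1 allows consent after treatment and retrospective data collection. A site could therefore be choosing between 5.4 and 5.5 when it already knows how the procedure went. A later analysis plan can define a sample, but it cannot recover a 90-day mRS or an adverse event that was never recorded.

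**Working it through.** **Step 1. Run each type of treated patient through the rules.**

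| Patient treated with SOFIA | 5.4 | ITT by 9.2.1(a) | ITT by 5.5 | PP by 9.2.1(b) |
|---|---|---|---|---|
| Meets all criteria | enrolled | in | not addressed | in, if no other listed deviation |
| Violation found after enrolment | enrolled | in | in | out |
| Knowingly treated outside the criteria | not enrolled | out | in | out |

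Only the last row conflicts. In the second row the sections agree. Violations can surface late: the core lab reads baseline ASPECTS and occlusion site for all participants (7 and 10.5), and the pregnancy test in 5.3 is recommended rather than mandatory.

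**Step 2. Reproduce the planned precision (9.1).** Inputs: expected rate p = 0.326, n = 236, two-sided 95%.

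Half-width = 1.96 × √(p(1 − p)/n) = 1.96 × √(0.326 × 0.674/236) = 0.0598, or ±5.98 points. The stated ±6.0% reproduces.

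**Step 3. Effect of omitting one patient.** Assumptions: 250 patients including the omitted one, and a rate of 32.6% among the others.

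- Omitted patient has mRS ≤ 2: (1/250) × (1 − 0.326) = 0.270 points; the reported rate is too low by this much.
- Omitted patient has mRS > 2: (1/250) × 0.326 = 0.130 points; the reported rate is too high by this much.

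**Step 4. How many omissions would exceed 6 points?**

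- All with mRS ≤ 2: 22 × 0.2696 = 5.93 and 23 × 0.2696 = 6.20, so 23 patients (23/250 = 9.2%).
- All with mRS > 2: 46 × 0.1304 = 5.998 and 47 × 0.1304 = 6.13, so 47 patients (47/250 = 18.8%).

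A mixture of outcomes would partly cancel, so these counts are the least that could do it.

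**Step 5. Kept in ITT but not followed.** Under the worst-case and best-case assignments of 9.2.2, each ITT patient without a 90-day mRS widens the range between the two by 1/250 = 0.4 points.

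**The case against.** The strongest reply is that 5.5 is part of the same protocol and is the specific rule for exactly these patients. Read with the first PP exclusion, it gives a complete answer: in ITT, out of PP. That stands as a reading of intent. It defeats the inference, tempting from 5.4 and 9.2.1(a) alone, that these patients fall outside both samples; that follows only if 5.5 is ignored.

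A reader might also infer that the eligibility item in the PP definition would remove nobody if enrolment required full eligibility. This is not so. If, say, the site scores ASPECTS 6 and the core lab's score of 5 is taken as a violation, the patient is already enrolled, stays in ITT and leaves PP.

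A third inference is that treated but ineligible patients lose follow-up as screen failures. The protocol does not say so. Section 5.1 describes evaluation before recruitment, 5.2 asks only for a log entry, and the 90-day mRS is routine practice under 5.10. What remains is that the log sentence is not limited to untreated patients, so the protocol does not rule this handling out.

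Finally, enrolling everyone in whom the catheter is inserted would be too broad a remedy. The device is in routine use, and 4.3 defines the study population by the criteria; unrelated uses should not be drawn in. That objection is right, and the fix is limited accordingly.

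None of this removes the contradiction. Knowing the intended sample does not help if a site following 5.4 has given the patient no number.

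**Conclusion.** Wrong as written; minor severity. Section 5.4 with 9.2.1(a) and section 5.5 give incompatible rules for patients knowingly treated outside the criteria. ITT and safety membership can therefore depend on the section a site applies.

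The size is modest: 0.13 to 0.27 points per omitted patient, on the assumptions of n = 250 and 32.6% among the rest. At least 23 omissions, all with the same favourable outcome, would be needed to exceed the planned precision. How many such patients there will be is not in the protocol. No loss of patients and no large bias is shown, and the sample-size calculation is unaffected. The issue is a consistent denominator, above all for safety.

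**What to change.** Make 5.5 the governing rule and align the other sections with it:

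- **9.2.1(a):** define ITT as all consented patients in whom a SOFIA or SOFIA PLUS catheter was inserted for first-line aspiration under the study, including those with an eligibility violation, with a cross-reference to 5.5.
- **5.4:** number such patients at insertion, record the violation and follow them to day 90. State whether they count toward the 250.
- **5.1 and 5.2:** limit screen failure to patients in whom no SOFIA catheter was inserted.
- **9.2.1(b):** leave the PP exclusions as they are.
- **Synopsis:** replace per protocol as the sole analysis population with the two samples of 9.2.1.

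The cost is a set of wording changes through the amendment route in 10.3.2, plus follow-up to day 90 for each added patient. No new type of assessment is needed. The total follow-up cost cannot be stated because the number of such patients is unknown.
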